### 6.7 Blinding and Procedures for Un-Blinding the Study

This is an open-label study, and there are no blinding/un-blinding procedures.

## 6.8 Permitted and Restricted Concomitant Medications

In general, medications or vaccinations specifically prohibited in the exclusion criteria are not allowed during the ongoing trial. Treatment with antacids, proton pump inhibitors and histamine receptor 2 inhibitors can be initiated as rescue therapy after patients have been receiving BGB324 for one week, provided they are taken in the evening.

If there is a clinical indication for any medication or vaccination specifically prohibited during the trial, discontinuation from trial therapy or vaccination may be required. The investigator should discuss any questions regarding this with the Sponsor Clinical Director. The final decision on any supportive therapy or vaccination rests with the investigator and/or the patient's primary physician. However, the decision to continue the patient on trial therapy or vaccination schedule (see [Section 6.10](#)) requires the mutual agreement of the investigator, the Sponsor and the patient.

Patients should not receive BGB324 during periods of systemic corticosteroid treatment. If a patient requires treatment with systemic corticosteroids, BGB324 should be interrupted immediately. Treatment with BGB324 may be restarted upon completion of systemic corticosteroid therapy. BGB324 may be continued at the appropriate dosage during periods of topical and inhaled corticosteroid therapy.

Hormonal contraception for female breast cancer patients is contraindicated.

## 6.9 Acceptable Concomitant Medications

All treatments that the Investigator considers necessary for a patient's welfare may be administered at the discretion of the Investigator in keeping with the community standards of medical care. All concomitant medication will be recorded on the CRF including all prescription, over-the-counter, herbal supplements, and i.v. medications and fluids. If changes occur during the trial period, documentation of drug dosage, frequency, route, and date may also be included on the CRF.

All concomitant medications received within 30 days before the first dose of trial treatment and 30 days after the last dose of trial treatment should be recorded. Concomitant medications administered after 30 days after the last dose of trial treatment should be recorded for SAEs and Events of Clinical Interest (ECIs) as defined in [Section 7.4.3.2](#).

## 6.10 Prohibited Concomitant Medications Whilst Receiving Pembrolizumab

Patients are prohibited from receiving the following therapies during the Screening and Treatment period (including retreatment for post-complete response relapse) of this trial:

- Antineoplastic systemic chemotherapy or biological therapy
- Immunotherapy not specified in this protocol
- Chemotherapy not specified in this protocol
- Investigational agents other than BGB324 and pembrolizumab
- Radiation therapy
  - Note: Radiation therapy to a symptomatic solitary lesion or to the brain may be considered on an exceptional case by case basis after consultation with Sponsor.

The patient must have clear measurable disease outside the radiated field. Administration of palliative radiation therapy will be considered clinical progression for the purposes of determining PFS. *Note: Treatment with pembrolizumab and BGB324 must have been discontinued at least one week prior to radiotherapy and should not be restarted within one week of completing radiotherapy.*

- Live vaccines within 30 days prior to the first dose of trial treatment and while participating in the trial. Examples of live vaccines include, but are not limited to, the following: measles, mumps, rubella, chicken pox, yellow fever, rabies, BCG, and typhoid (oral) vaccine. Seasonal influenza vaccines for injection are generally killed virus vaccines and are allowed. However, intranasal influenza vaccines (e.g. Flu - Mist®) are live attenuated vaccines, and are not allowed.
- Systemic glucocorticoids for any purpose other than to modulate symptoms from an event of clinical interest of suspected immunologic etiology. If a patient requires physiologic doses of corticosteroids, they must discontinue their BGB324.
  - Note: Inhaled steroids are allowed for management of asthma.

Patients who, in the assessment by the investigator, require the use of any of the aforementioned treatments for clinical management should be removed from the trial. Patients may receive other medications that the investigator deems to be medically necessary.

The Exclusion Criteria describes other medications that are prohibited in this trial.

There are no prohibited therapies during the Follow Up period once the patient has discontinued both treatments.

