- Treatment non-compliance. (All documentation concerning the patient must be as complete as possible. Withdrawals due to non-attendance of study visits must be followed-up by the Investigator to obtain the reason for where possible. For further information on treatment non-compliance, please see also [Section 3.5](#)).
- Pregnancy.

A patient is defined as 'lost to follow-up' only if every effort has been made to contact the patient and determine the patient's willingness to continue with all or some of the study assessments (irrespective of whether the patient is still receiving study treatment).

**Patients who are unwilling to continue to receive further treatment are expected to continue in follow-up to enable assessment of the duration of their response and other endpoints until confirmed progression and then survival status.**

The Sponsor reserves the right to request the withdrawal of study treatment from a patient due to protocol violation or other significant reason.

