### **3.6 Procedures for Patient Cessation of Study Treatment**

When a patient stops or discontinues one or both of their study treatments, the reason for cessation will be recorded in the patient file and the Case Report Form (CRF). Patients must complete a post treatment visit, and continue with their scans and assessments of disease (if the patient has not already progressed) and/or survival status.

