### 5.3.10 Tumor imaging

Efficacy endpoints in this study, including ORR, DoR, PFS will all be based on tumor imaging evaluation by RECIST 1.1.

RECIST assessments will be performed at the times given in Schedule of Study Assessment Table 4 and Table 5 using contrast-enhanced CT (preferred method) or MRI assessments of chest, abdomen, and pelvis. X-ray scans can be used where appropriate. Bone scans and brain scans should be conducted in the 6 weeks prior to study entry. Subsequently, x-ray, bone scans and brain scans will be used as appropriate. Additional anatomy should be imaged based on signs and symptoms of individual patients at baseline and follow-up.

Baseline assessments should be performed no more than 28 days before start of study treatment (6 weeks for brain and bone scans), and ideally should be performed as close as possible to the start of study treatment. The Screening imaging assessments must confirm the patient has measurable disease per RECIST 1.1 (see [Section 3.1](#)).

For each patient, the same modality used at Screening must be used serially throughout the duration of study participation. All imaging procedures will be performed according to standard local imaging protocols to ensure consistency across study assessments.

All radiological and non-radiological (e.g. MRI) scans will be reviewed by the local site investigator; and if possible, stored electronically (de-identified with the patient's notes) at site.

A maximum of 5 target lesions (TLs) must be selected at baseline. All target lesions are measurable. Target lesions should be selected on the basis of their size (longest diameter for non-nodal lesions or short axis for nodal lesions), but in addition should be those that lend themselves to reproducible repeated measurements. All remaining lesions present at baseline are considered non-target, irrespective of whether they are measurable.

Disease assessments will be performed as per the schedule described in [Table 3](#), [Table 4](#) and [Table 5](#) – that is, every 9 weeks  $\pm 7$  days for the first 46 weeks relative to the date of first treatment administration and then every 12 weeks  $\pm 7$  days thereafter until confirmed objective disease progression as defined by RECIST 1.1 (irrespective of a delay to treatment, or the reason for stopping treatment or subsequent therapy).

Any other sites at which new disease is suspected should also be adequately imaged at a follow-up visit.

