### 8.12.2.3 Progression free survival and overall survival

Kaplan Meier plots of the time to progression and death will be presented, along with the median progression free survival and the estimated survival at 12 months. Descriptive statistics will be used as required, including 95% CI.

PFS is measured from the date of the 1st dose of the 1st cycle until the date of progression (the date on which the progression is initially observed) or the date of death (whichever is earlier). Patients who have not progressed or died before the date of data cut-off (last patient, last visit) will be censored at their last clinical evaluation.

The estimated survival at 12 months will be read from the Kaplan Meier OS curve. The time to death is defined as the time from the date of enrolment until the date of death (from any cause and irrespective of any subsequent ant-cancer treatment given). Patients who remain known to be alive at the date of data cut-off (last patient, last visit) will be censored at their date last known to be alive. Patients who are lost to follow-up will be censored at the point last known to be alive; however, if  $\geq 2\%$  of patients are in this category, a sensitivity summary will be produced to illustrate the overall survival assuming the patient died at the date last known in the trial. If possible, the date of death may be recovered from publically available sources such as death registries.

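### Section 6.10 takes patients who need a prohibited treatment out of the trial, although the follow-up sections keep patients who stop treatment in imaging and survival follow-up

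*Protocol*

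**What the plan says.** Section 6.10 opens with its scope: "Patients are prohibited from receiving the following therapies during the Screening and Treatment period". The list covers systemic chemotherapy and biological therapy, other immunotherapy, investigational agents, radiotherapy, live vaccines and systemic glucocorticoids. It then says that patients who, in the investigator's assessment, "require the use of any of the aforementioned treatments for clinical management should be removed from the trial".

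The same section contains three statements that bear on this:
- Exceptional radiotherapy may be considered case by case after consultation with the sponsor, and the note includes a condition on restarting study drug. It adds: "Administration of palliative radiation therapy will be considered clinical progression for the purposes of determining PFS".
- The glucocorticoid entry has its own carve-out and, for physiologic doses, speaks of discontinuing BGB324 only.
- It closes: "There are no prohibited therapies during the Follow Up period once the patient has discontinued both treatments".

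Elsewhere in the protocol:
- Section 6.8, on the need for a prohibited medication, says that stopping trial therapy may be required. It does not speak of leaving the trial.
- Section 3.3 separates withdrawal from treatment from withdrawal from participation. Patients who decline only further treatment "are expected to continue in follow-up to enable assessment of the duration of their response and other endpoints", until confirmed progression and then for survival.
- Section 3.6: patients who stop one or both drugs "continue with their scans and assessments of disease (if the patient has not already progressed) and/or survival status".
- Section 5.3.10: imaging runs to confirmed progression "irrespective of a delay to treatment, or the reason for stopping treatment or subsequent therapy". Section 8.5 repeats the rule in almost the same terms.
- Section 8.12.2.3: deaths count from any cause and "irrespective of any subsequent ant-cancer treatment given".

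**The concern.** The protocol distinguishes stopping treatment from leaving the study, and its endpoints depend on that distinction. The 6.10 sentence ignores it. Read as written, it ends scans and survival contact for a patient whom Sections 3.6, 5.3.10 and 8.5 require the site to keep following.

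The need for new systemic anti-cancer therapy during treatment is plausibly related to prognosis. If follow-up stops at that moment, censoring is no longer independent of the outcome, and Kaplan-Meier estimates of PFS, duration of response and overall survival tend to come out too high. Section 8.2.2 lists duration of response and PFS, where available, among what the Data Review Committee weighs at the end of Stage 1.

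The primary endpoint can also be touched, in the other direction. Responses need a confirmatory scan at least 28 days later, and Section 8.11 allows later scans to be used after an apparent progression. A patient removed before those scans could be missed as a responder.

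**Working it through.** **1. Which rule applies to a patient who needs a listed treatment while on study drug**

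| Question | Section 6.10 sentence | Rest of the protocol |
|---|---|---|
| Study treatment | Ends, by implication | 6.8: may have to stop. The 6.10 radiotherapy note envisages a restart; its physiologic-dose corticosteroid note names BGB324 only |
| Imaging | Ends | 3.6, 5.3.10, 8.5: continues to confirmed progression |
| Survival contact | Ends | 3.6, 8.12.2.3: continues; deaths count after later therapy |
| Later therapy | No provision | 6.10 closing sentence: unrestricted in Follow Up; Section 5.1.1 schedules its collection there |

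Both columns cannot be followed for the same patient.

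**2. What happens in the analysis**

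Section 8.4 defines an evaluable patient by one combination dose and measurable disease at entry, so a removed patient stays in the efficacy population. Under 8.12.2.3 the patient is censored at the last clinical evaluation (PFS) or when last known alive (OS). Palliative radiotherapy is already a PFS event, so for that group the loss mainly concerns OS.

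**3. The design figures do not depend on this sentence**

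With n1 = n2 = 28, the probability of rejecting the null is P(X1 ≥ 11) + Σ over x = 6 to 10 of P(X1 = x)·P(X2 ≥ 17 − x).

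| Quantity | Stated in 8.1 | Exact |
|---|---|---|
| Type I error at 0.20 | 0.048 | 0.0483 |
| Power at 0.35 | 80.6% | 80.5% |
| Futility stop under the null | 50.2% | 50.1% |
| Activity stop under the alternative | 38.4% | 38.4% |
| Expected sample size | 42-44 | 41.6 and 44.1 |

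The stated figures are reproduced to within simulation error. The response-rate denominator is fixed by 8.4.

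**4. Illustration for 12-month OS**

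The only input from the protocol is the 13-month median survival in Section 1.1. The assumptions are: exponential survival with that median applied from first dose; a fraction f selected for removal, at a time U uniform over months 1 to 6 if still alive; and a death hazard multiplied by h from then on.

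- λ = ln 2 / 13 = 0.0533 per month; S = exp(−12λ) = 0.527. Everyone has hazard λ until removal, so Kaplan-Meier with censoring at removal estimates S whatever f is.
- True 12-month survival is (1 − f)S + fR, where R = E[exp(−λU − hλ(12 − U))] = exp(−12hλ) × [exp(6(h−1)λ) − exp((h−1)λ)] / [5(h−1)λ].
- h = 2: R = 0.2781 × 1.2087 = 0.336, so S − R = 0.191.
- h = 3: R = 0.1467 × 1.4697 = 0.216, so S − R = 0.312.
- h = 1: R = S, so there is no bias.

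The overstatement is f(S − R):

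| f | h = 1 | h = 2 | h = 3 |
|---|---|---|---|
| 5% | 0 | 1.0 points | 1.6 points |
| 10% | 0 | 1.9 points | 3.1 points |
| 20% | 0 | 3.8 points | 6.2 points |

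A simulation of 400,000 patients agrees to within 0.1 point. A different assumption, in which a random 10% are censored 2 to 4 months before death, gives 55.5-55.9% against a true 52.7%. With 20% it gives 58.7-59.2%.

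**5. The protocol's OS sensitivity summary**

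Section 8.12.2.3 counts patients lost to follow-up as deaths when they reach 2% or more. At 56 patients that takes two (1/56 = 1.8%, 2/56 = 3.6%). In the first model with f = 10% it gives 0.9 × 0.527 = 47.5%. The true value is 50.8% (h = 2) or 49.6% (h = 3), and the main estimate is 52.7%, so the two estimates bracket the truth.

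**The case against.** The best defence is that removal was only meant as removal from treatment. Section 6.10 is headed as applying during pembrolizumab, covers Screening and Treatment only, and ends by allowing any therapy in Follow Up. Section 3.3 states continued follow-up twice in bold, Section 3.6 makes it mandatory, and the schedule collects subsequent anti-cancer treatment. Patients with confirmed progression stop study therapy and enter Follow Up, so the usual switch to chemotherapy is not caught. That intent is plausible. It does not cure the sentence, which is the instruction a site reads when the situation arises. Scans not taken cannot be recovered, and death dates may be sought from public sources only where possible.

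Some further limits stand in full:
- Vaccines and some steroid use need not mark a poor prognosis.
- Section 3.3 concerns patients who decline further treatment. It does not say that later therapy is irrelevant; that wording is in 5.3.10, 8.5 and, for deaths, 8.12.2.3.
- Section 8.2.2 does not name OS among what the committee weighs, and OS is the only endpoint quantified here.
- The sensitivity summary helps OS, but only if removed patients are classed as lost to follow-up. It does not cover PFS or duration of response.
- The 13-month median runs from the appearance of metastatic disease, not from enrolment after earlier metastatic therapy.

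A reader might infer that the worst-prognosis patients are dropped from the PFS, duration-of-response and survival analyses. The documents do not support that. These patients stay evaluable and are censored, palliative radiotherapy is counted as progression, radiotherapy has a case-by-case exception, and not everyone on the list is doing badly.

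**Conclusion.** The contradiction is real and should be corrected. It is a conflict of wording, not a flaw in the two-stage design. Literal compliance ends imaging and survival contact early for some patients on treatment, and their censoring is then likely to depend on prognosis. The expected direction is upward for PFS, duration of response and 12-month OS, with a possible missed response in the primary endpoint.

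The protocol does not determine the size. Roughly 2 to 6 points on 12-month OS follows from assumed removal of 10% to 20% and a doubled or tripled hazard afterwards; the bias is zero if the hazard does not change. The removal shares, removal times and hazard ratios are all assumptions, and the bias in PFS and duration of response has not been quantified. Type I error, power, sample size and the response-rate denominator do not change.

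**What to change.** Amend the 6.10 sentence so that it separates discontinuation of study treatment from the end of study participation. It should say that such patients remain in the already scheduled imaging until confirmed progression, and in survival follow-up, as Sections 3.6, 5.3.10 and 8.5 provide, unless they withdraw consent to participation. In the same edit, reconcile the sentence with Section 6.8 and with 6.10's own radiotherapy and corticosteroid notes. Which situations require treatment to stop is a clinical matter and is not addressed here.

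Separately, on pregnancy, Section 6.14.1 has the patient leave the study while Section 7.5 has her withdrawn from study treatment with follow-up agreed with the sponsor. Those two passages must be reconciled; no rule is proposed.

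The cost is a short text change in an amendment. The visits, scans and survival contacts are already in the schedule, and neither the sample size nor the decision rules are affected.

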## 6.11 Supportive Care Guidelines for Pembrolizumab

Patients should receive appropriate supportive care measures as deemed necessary by the treating investigator. Suggested supportive care measures for the management of AEs with potential immunologic etiology are outlined below. Where appropriate, these guidelines include the use of oral or intravenous treatment with corticosteroids as well as additional anti-inflammatory agents if symptoms do not improve with administration of corticosteroids. Patients receiving oral or intravenous corticosteroids must interrupt treatment with BGB324 throughout the duration of therapy.

Note that several courses of steroid tapering may be necessary as symptoms may worsen when the steroid dose is decreased. For each disorder, attempts should be made to rule out other causes such as metastatic disease or bacterial or viral infection, which might require additional supportive care. The treatment guidelines are intended to be applied when the investigator determines the events to be related to pembrolizumab.

Note: If after the evaluation the event is determined not to be related, the investigator does not need to follow the treatment guidance (as outlined below). Refer to [Section 6.6](#) for dose modification.

It may be necessary to perform conditional procedures such as bronchoscopy, endoscopy, or skin photography as part of evaluation of the event.

- **Pneumonitis:**

- For **Grade 2 events**, treat with systemic corticosteroids. When symptoms improve to Grade 1 or less, steroid taper should be started and continued over no less than 4 weeks.
- For **Grade 3-4 events**, immediately treat with i.v. steroids. Administer additional anti-inflammatory measures, as needed.
- Add prophylactic antibiotics for opportunistic infections in the case of prolonged steroid administration.
- **Diarrhea/Colitis:**  
Patients should be carefully monitored for signs and symptoms of enterocolitis (such as diarrhea, abdominal pain, blood or mucus in stool, with or without fever) and of bowel perforation (such as peritoneal signs and ileus).
  - All patients who experience diarrhea/colitis should be advised to drink liberal quantities of clear fluids. If sufficient oral fluid intake is not feasible, fluid and electrolytes should be substituted via i.v. infusion. For Grade 2 or higher diarrhea, consider GI consultation and endoscopy to confirm or rule out colitis.
  - For **Grade 2 diarrhea/colitis** administer oral corticosteroids.
  - For **Grade 3 or 4 diarrhea/colitis**, treat with intravenous steroids followed by high dose oral steroids.
  - When symptoms improve to Grade 1 or less, steroid taper should be started and continued over no less than 4 weeks.
- **Type 1 diabetes mellitus (if new onset, including diabetic ketoacidosis [DKA]) or  $\geq$  Grade 3 hyperglycemia, if associated with ketosis (ketonuria) or metabolic acidosis (DKA)**
  - For **T1DM or Grade 3-4 hyperglycemia**
    - Insulin replacement therapy is recommended for Type I diabetes mellitus and for Grade 3-4 hyperglycemia associated with metabolic acidosis or ketonuria.
    - Evaluate patients with serum glucose and a metabolic panel, urine ketones, glycosylated hemoglobin, and C-peptide.
- **Hypophysitis:**
  - For **Grade 2 events**, treat with corticosteroids. When symptoms improve to Grade 1 or less, steroid taper should be started and continued over no less than 4 weeks. Replacement of appropriate hormones may be required as the steroid dose is tapered.
  - For **Grade 3-4 events**, treat with an initial dose of i.v. corticosteroids followed by oral corticosteroids. When symptoms improve to Grade 1 or less, steroid taper should be started and continued over no less than 4 weeks. Replacement of appropriate hormones may be required as the steroid dose is tapered.
- **Hyperthyroidism or Hypothyroidism:**  
Thyroid disorders can occur at any time during treatment. Monitor patients for changes in thyroid function (at the start of treatment, periodically during treatment, and as indicated based on clinical evaluation) and for clinical signs and symptoms of thyroid disorders.
  - **Grade 2** hyperthyroidism events and **Grade 2-4** hypothyroidism:

- In hyperthyroidism, non-selective beta-blockers (e.g. propranolol) are suggested as initial therapy.
- In hypothyroidism, thyroid hormone replacement therapy, with levothyroxine or liothyroinine, is indicated per standard of care.
- **Grade 3-4** hyperthyroidism
  - Treat with an initial dose of i.v. corticosteroid followed by oral corticosteroids. When symptoms improve to Grade 1 or less, steroid taper should be started and continued over no less than 4 weeks. Replacement of appropriate hormones may be required as the steroid dose is tapered.
- **Hepatic:**
  - For **Grade 2** events, monitor liver function tests more frequently until returned to baseline values (consider weekly).
    - Treat with IV or oral corticosteroids
  - For **Grade 3-4** events, treat with i.v. corticosteroids for 24 to 48 hours.
  - When symptoms improve to Grade 1 or less, a steroid taper should be started and continued over no less than 4 weeks.
- **Renal Failure or Nephritis:**
  - For **Grade 2** events, treat with corticosteroids.
  - For **Grade 3-4** events, treat with systemic corticosteroids.
  - When symptoms improve to Grade 1 or less, steroid taper should be started and continued over no less than 4 weeks.
- **Management of Infusion Reactions:** Signs and symptoms usually develop during or shortly after drug infusion and generally resolve completely within 24 hours of completion of infusion.

